9.3.2. Response Rate

The proportion of patients achieving response (CR+PR) is a secondary endpoint for the safety LIC. A confirmation of response (Peripheral Blood only) is required 4 weeks after the first assessment per IWG 2006. The final analyses will be conducted after all patients in the safety LIC have been followed for 28 weeks (to allow for confirmation of response per IWG 2006). The proportion and two-sided 95% CI (using exact method) of patients achieving response (CR+PR) will be provided for the safety LIC.

9.3.3. Overall Survival (Expansion)

Overall survival (OS) is defined as the time from date of first study treatment to date of death due to any cause. Patients last known to be alive will be censored at the date of last contact.

OS will be analyzed and displayed graphically for each expansion cohort separately using the Kaplan-Meier method. The median event time for each expansion cohort and corresponding two-sided 95% CI will be provided. The Kaplan-Meier estimate of survival probabilities at 12, 18, and 24 months and their two-sided 95% CI (using log-log transformation and back-transformation) will be provided for each arm separately.

First, OS will be analyzed when the primary endpoint of CR is analyzed in the respective expansion cohort. A follow-up analysis of updated OS will be conducted when the study concludes. OS is defined as the date of the first dose of any of the study medications to the date of death from any cause.

9.3.4. Duration of Response

Duration of Response (DoR) is only defined in MDS patients or AML patients achieving a CR in the expansion component. DoR is defined as the duration from date of first achieving CR to the date of disease progression (relapse) after CR, or death due to any cause. Patients last known to be alive who are free from disease progression or relapse after CR are censored at the date of the last assessment that verifies their disease status. The minimum DoR is 4 weeks for MDS patients by definition (CR must last at least 4 weeks to qualify as such per [Appendix 2](#)).

DoR will be analyzed and displayed graphically for each expansion cohort separately using the Kaplan-Meier method. The median DoR and corresponding two-sided 95% CI will be provided.

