30. **Follow Up Activity Log: Survival Follow-Up Telephone contact, New Anti-cancer therapies since discontinuation of study treatment, and Disease progression:** A follow-up contact (can be by phone) per Section 6.4 should occur at least 28 calendar days, and up to 35 calendar days after the last administration of the investigational product to capture any potential adverse events (Section 6.4). Appropriate contraception useage for at least 180 days after the last dose of investigational product is to be confirmed. Patients will be contacted by telephone every 3 months starting from the last dose of study medication to confirm survival status, collect information on any new anti-cancer therapies initiated and record date of post-treatment disease progression. CCI
Patients receiving at least one dose of study treatment will be followed for survival for up to 2 years from the first visit of the last patient enrolled in the expansion component, or until death, lost to follow up, or consent withdrawal.

CCI

Table 4. Pharmacokinetics & ECG Schedule for the Expansion: MDS and AML Patients

Assessment	Screening	Cycle 1, Day 1			Cycle 1, Day 15			Cycle 2-3, Day 1 ³			Cycles ≥4, Day 1	End of treatment
HOURL post-dose ¹		0 ¹	1	4	0 ¹	1	4	0 ¹	1	4	1	
Glasdegib PK Plasma Samples			X	X	X	X	X	X	X	X		
Triplicate 12-lead ECG ²	X	X	X	X	X	X	X	X	X	X	X	X

- Glasdegib PK Sample Collection:** In all instances, “0 hour” represents a pre-dose collection. The PK sample should be collected within 30 minutes prior to dose administration. All post-dose samples are to be collected within 10% of the nominal time (eg, within 6 minutes of a 60 minute sample). Patients should be reminded not to take their study drug prior to arriving at the clinic on protocol scheduled visits. All PK timepoints are in reference to dosing of glasdegib.
- Triplicate 12-Lead ECGs:** At each time point, 3 consecutive supine 12-lead ECGs will be performed approximately 2 minutes apart to determine mean QTc interval. ECGs will be collected: prior to blood sample collection, such that the blood sample is collected at the appropriate time. All ECG timepoints are in reference to dosing of glasdegib). A 15 min window for each ECG collection is allowed around the nominal ECG time point.
- PK samples to be collected only on Cycle 2 Day 1.

TABLE OF CONTENTS

LIST OF TABLES	50
LIST OF FIGURES	50
APPENDICES	50
1. INTRODUCTION	52
1.1. Indication.....	52
1.2. Background and Rationale	52
1.2.1. Disease Overview	52

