6.4. Follow-up

The first follow up contact should occur at least 28 days, and no more than 35 days after the last dose of study drug to capture any potential adverse events (refer to [Section 8.2](#)) and to confirm appropriate contraception usage (refer to [Section 4.3](#)). Contact with the patient may be done via phone. For a detailed list of assessments and procedures to be completed please refer to the [Schedule of Activities for the Safety Lead-in](#) and the [Schedule of Activities for the Expansion: MDS and AML Patients](#).

In cases of unacceptable toxicity or pregnancy, the patient must be withdrawn from study drug combination and entered into the follow-up phase of the study.

Patients who permanently discontinue both study drugs (azacitidine and glasdegib) for any reason (except death, or withdrawal of patient consent) will enter into the follow-up phase.

Patients continuing to experience toxicity following discontinuation of treatment will continue to be followed minimally every 4 weeks until resolution or determination, in the clinical judgment of the Investigator, that no further improvement is expected.

Patients enrolled in the safety LIC, which has been completed, will be contacted every 3 months to confirm survival status, and to collect information on any new anti-cancer therapy initiated. Telephone calls are acceptable and patients will be followed up to the time of death or consent withdrawal. Patients starting the study long-term follow up phase with $\leq 30\%$ BM blasts should also have disease assessments (BM aspirate and PB sampling) until blasts are $>30\%$ or until initiation of another anti-cancer therapy.

Patients enrolled in the expansion component will be contacted every 3 months to confirm survival status, and to collect information on any new anti-cancer therapy initiated. Date of post-treatment disease progression recorded in the source notes will be collected. CCI

Patients receiving at least one dose of study treatment will be followed for survival for up to 2 years from the first visit of the last patient enrolled in the expansion component, or until death, lost to follow-up, or consent withdrawal.

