7.7. Efficacy Assessments

7.7.1. Response Criteria

Disease response, measured from baseline through the End of Treatment, will be evaluated using IWG Modified Response Criteria ([Appendix 2](#)) for all patients in the Safety Lead-In cohort and for the MDS patients in the Expansion. The 2017 ELN Response Criteria will be applied to all AML patients in the Expansion ([Appendix 11](#)).

CR with partial hematologic recovery (CRh) will be assessed for the AML Expansion Cohort. CRh is defined as CR but with ANC $>$ 0.5x10⁹/L and platelets $>$ 50x10⁹/L.

CCI

CCI

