6.1.3. Time to event endpoints

- **OS**

OS is defined as the time from date of the first dose of any of the study medications to date of death due to any cause. Patients last known to be alive will be censored at the date of last contact. OS will be summarized in months:

OS (months) = [date of death or censoring–date of the first dose +1]/30.4375.

- **Duration of complete response (DoCR)**

DoCR is only defined in MDS patients or AML patients achieving a CR in the expansion component. DoCR is defined as the duration from date of first achieving CR to the date of disease progression (relapse) after CR, or death due to any cause. Patients last known to be alive who are free from disease progression or relapse after CR are censored at the date of the last assessment that verifies their disease status. The minimum DoCR is 4 weeks by definition (CR must last at least 4 weeks to qualify as such per IWG 2006) for MDS patients.

- **Duration of response (CR+PR)**

Duration of Response (DoR) (including CR+PR) is defined for patients in Safety LIC and the expansion cohort who have ever achieved CR or PR on study as the time from date of first achieving CR or PR to the date of disease progression, or relapse after CR/PR, or death due to any cause. Patients last known to be alive who are free from disease progression or relapse after CR/PR are censored at the date of last disease assessment that verifies their status. Note that minimum DoR is 4 weeks by definition (CR/PR must last at least 4 weeks to qualify as such per IWG 2006) for MDS patients.

- **CCI**

[REDACTED]

- **Time to Response (CR)**

Time to response (TTR) is only defined for patients in the expansion component of the study who have ever achieved CR on study as the time from date of the first dose of study drug to date of the first documentation of response (CR). Note that response needs to be confirmed by definition (CR must last at least 4 weeks to qualify as such per IWG 2006) for MDS patients.

- **CCI**

[REDACTED]

CCI [REDACTED]

[REDACTED]

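### In the expansion, duration of CR counts relapse or death after treatment but, unless a progression-free contact counts as an assessment, gives no credit for time in remission off treatment, which tends to shorten the estimate

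*Protocol*

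**What the plan says.** Events. Protocol 9.3.4 runs duration of CR from first CR "to the date of disease progression (relapse) after CR, or death due to any cause". Nothing limits events to the treatment period. SAP 6.1.3 repeats the definition.

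Censoring. Patients alive and free of relapse "are censored at the date of the last assessment that verifies their disease status"; the SAP uses the same words for duration of CR. For duration of CR+PR the SAP says that they "are censored at the date of last disease assessment that verifies their status". Overall survival is handled differently in protocol 9.3.3: "Patients last known to be alive will be censored at the date of last contact".

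Assessment after treatment. Protocol 7.7.1 covers "Disease response, measured from baseline through the End of Treatment". Table 3 has no hematology or marrow in its long-term follow-up column. Footnote 30 describes a telephone contact every 3 months to "confirm survival status, collect information on any new anti-cancer therapies initiated and record date of post-treatment disease progression". Section 6.4 names the source: "Date of post-treatment disease progression recorded in the source notes will be collected". Footnote 29 lets the End of Treatment marrow be skipped if one was done in the previous 3 months, unless the patient is leaving for progression.

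The lead-in differed. Under Table 1, footnote 29, patients who stopped both drugs with marrow blasts of 30% or less had marrow and blood assessments every 3 months, until blasts exceeded 30% or new therapy began.

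**The concern.** The two halves of the rule follow off-treatment patients for different lengths of time. Take two patients who stop both drugs in CR six months after reaching it. One relapses at month 14 and contributes 14 months and an event. The other is still in remission at month 20. If her last verifying assessment was at End of Treatment, she contributes 6 months. Among patients off treatment, follow-up beyond that point then depends on having an event. Kaplan-Meier assumes that censoring carries no information about the outcome, and here it does.

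Duration of CR is a secondary objective and endpoint in both expansion cohorts. The error would be systematic, so the planned 95% confidence interval would not reflect it. SAP 7.2 imputes nothing, and no sensitivity analysis for this censoring appears in the readable text.

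**Working it through.** The documents give no assumed duration of CR, no stopping rate and no accrual period, so there is no planned figure to reproduce. Every numerical input below is an assumption.

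**Inputs.** Time from CR to relapse or death is exponential with median 12 months: λ = ln 2/12 = 0.0578 per month. Stopping both drugs while in CR is independent of relapse, with share p stopped by month 12: δ = −ln(1−p)/12. Every relapse or death before the data cut c (months after CR) is recorded.

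**Mechanism.** At time t the proper at-risk proportion is e^(−λt). Under the rule read literally it is (e^(−λt) − e^(−λc)) + e^(−λc)·e^(−δt). The first part is patients whose event is still to come before the cut. The second is patients who will be event-free at the cut and are still on treatment at t. The hazard is therefore multiplied by e^(−λt) divided by that sum.

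For t = 6 and c = 12, e^(−λt) = 0.7071 and e^(−λc) = 0.5:
- p = 0: 0.2071 + 0.5 × 1 = 0.7071; ratio 1.00
- p = 10%: 0.2071 + 0.5 × 0.9487 = 0.6815; ratio 1.04
- p = 30%: 0.2071 + 0.5 × 0.8367 = 0.6254; ratio 1.13
- p = 50%: 0.2071 + 0.5 × 0.7071 = 0.5607; ratio 1.26

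**Size at an early cut.** Large-sample Kaplan-Meier simulation with the cut uniform from 2 to 14 months after CR:

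| Stop both drugs in CR by month 12 | Median (true 12.0) | 12-month rate (true 50%) | Loss |
|---|---|---|---|
| 0% | 12.0 | 50% | none |
| 10% | 11.5 | 48% | about 0.5 months, 2 points |
| 30% | 10.5 | 45% | 1.5 months, 5 points |
| 50% | 9.6 | 39% | 2.4 months, 11 points |

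In these scenarios, both consistent rules recover the truth: crediting event-free time to the last known status, or ending everyone's follow-up at end of treatment.

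**Later cut (20 to 32 months after CR).** At 10% stopping: 11.8 months and 49%. At 50%: 10.9 months and 46%.

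**A second model.** Cut 6 to 30 months after CR, on-treatment relapse seen at the next 28-day visit, true median 12. With 10/20/30/50% stopping, the 12-month rate is 0.489/0.478/0.465/0.435 under the literal rule and 0.494 to 0.499 under either consistent rule. Changing one assumption at a time, at 30% stopping:
- Last verifying marrow 1.5 months before end of treatment: 0.456.
- Only half of post-treatment relapses or deaths captured: 0.479.
- On-treatment relapse seen only at scheduled marrows: 0.610, so the net estimate is too long. Censoring at last contact gives 0.636 in that setting, so the rule still lowers the estimate relative to a consistent one.

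**The case against.** The strongest reply is that the plan never says the last verifying assessment is the End of Treatment visit. Table 3 lists the post-treatment progression row under a heading that calls these items follow-up assessments, and the duration-of-CR wording does not require a marrow or a visit. If a contact that finds no progression counts, the asymmetry disappears. This stands as an ambiguity. Against it, overall survival is censored at last contact while duration of CR is not, the SAP's CR+PR rule says disease assessment, and no readable field holds a progression-free date. Text is redacted directly after the follow-up sentences in 6.4 and footnote 30, so the full content of the contact is not visible.

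A second reply is that if 7.7.1 confines the response criteria to the treatment period, post-treatment relapse might not count either. But 9.3.4 carries no such limit, and deaths would still count.

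Third, the size may be small. Section 5.4.4 directs treatment until progression or relapse, and allows azacitidine alone after glasdegib stops, so few may stop both drugs in CR. Sampling error is also large: assuming 12 CR patients, the standard deviation of the 12-month estimate is about 15 points at the late cut and 21 at the early one. This stands, and the endpoint is descriptive. The confidence interval, however, shows sampling error and not this bias.

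A reader might infer that after treatment the risk set holds only patients who will have an event. It does not: CR patients still on treatment remain in it. A reader might also infer that the reported duration is bound to be too short. The documents do not support that, because missed relapses and marrows up to 12 cycles apart push the other way. The marrow-only case above is extreme, since blood counts with blasts are taken every cycle.

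**Conclusion.** The point holds as a defect in the censoring rule as written, with a direction for that rule alone and not for the net error from all sources. Unless a progression-free contact counts as a verifying assessment, follow-up of CR patients off both drugs depends on outcome, and that tends to shorten the estimate. Under the early-cut assumptions the effect runs from nil to 2.4 months on the median and 11 points at 12 months. The upper end needs half of CR patients to stop both drugs without relapse by month 12, and nothing in the documents supports treating that as the expected case. The effect shrinks at a later cut. This is a worthwhile, inexpensive correction to a secondary endpoint. It does not touch the primary CR rate.

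**What to change.** At each planned 3-monthly contact, record for every patient who stopped treatment in CR (or in PR, for the CR+PR duration) either the relapse or progression date, or a statement that source notes show none as of a given date. In protocol 9.3.4 and in SAP 6.1.3, for both duration of CR and duration of CR+PR, state that event-free patients are censored at the latest such date or on-study assessment.

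If that date will not be collected, use the mirror rule: end every patient's follow-up at the last on-study disease assessment and do not count later events. Report the alternative rule as a sensitivity analysis.

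The cost is one field on an existing contact and a sentence in each document, with no added visit or marrow. Remission off treatment would be judged from local notes, as progression already is. If those notes miss events, the first rule errs long: with half captured and 30% stopping, the second model gives 0.531 against a true 0.50, while the mirror rule gives 0.496. The mirror rule discards late events.

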9.3.5. Time to Response

Time to response (TTR) is only defined for patients in the expansion component who have ever achieved response on study as the time from date of the first dose of study drug to date of the first documentation of response (CR+PR). Note that response needs to be confirmed for MDS patients by definition (CR must last at least 4 weeks to qualify as such per [Appendix 2](#)).

TTR will be analyzed and displayed graphically for each cohort separately using the Kaplan-Meier method. The median TTR and corresponding two-sided 95% CI will be provided.

9.3.6. Other Efficacy Measures

Additional efficacy measure of interest for the safety LIC and expansion MDS cohort include marrow CR (mCR), partial remission (PR), stable disease (SD), partial or complete cytogenetic response, and hematologic improvement (HI). Additional efficacy measures of interest for the expansion AML cohort include CR with incomplete hematologic recovery (CRi), complete remission with partial hematologic recovery (CRh), morphologic leukemia-free state (MLFS), PR, SD, Cytogenetic CR (CRc), and molecular CR (CRm) per [Appendix 11](#).

The proportion of patients ever achieving each of the endpoints for the respective cohort will be estimated with two-sided 95% CI respectively.

CCI
[Redacted text block]

CCI [REDACTED]

[REDACTED]

[REDACTED]

[REDACTED]

[REDACTED]

CCI [REDACTED]

[REDACTED]

[REDACTED]

CCI [REDACTED]

[REDACTED]

CCI [REDACTED]

[REDACTED]

CCI

9.4. Safety Analysis

Summary and analysis of the safety parameters will include all patients in the safety analysis set. They will be reported separately for the safety LIC and each cohort in the expansion, as well as all three cohorts pooled.

9.4.1. Adverse Events

9.4.2. Analysis of Primary Endpoint of Safety Lead-in Cohort

Overall safety profile and tolerability will be characterized by type, frequency, severity, timing, and relationship to study therapy of adverse events and laboratory abnormalities.

Adverse events will be classified using the MedDRA classification system. The severity of the toxicities will be graded according to the NCI CTCAE version 4.03.

In all summaries, emphasis will be placed on treatment emergent adverse events (TEAEs), namely, those with initial onset or that worsen in severity after the first dose of study drug. Adverse events will be summarized by the frequency of patients experiencing treatment emergent adverse events corresponding to body systems and MedDRA preferred term and by worst NCI CTCAE (version 4.03) grade. Summaries will also be provided of treatment related TEAEs, namely, those judged by the investigator to be related or likely related to study drug.

Adverse events leading to death or discontinuation of study treatment, events classified as NCI CTCAE version 4.03 Grade 3 or higher, study drug related events, and serious adverse events will be considered with special attention. Adverse events reporting, including suspected unexpected serious adverse reactions, will be carried out in accordance with applicable local regulations.

9.4.3. Analysis of Secondary Endpoint of Expansion Component

Overall safety profile will be characterized by type, frequency, severity, timing, and relationship to study therapy of adverse events and laboratory abnormalities.

Adverse events will be classified using the MedDRA classification system. The severity of the toxicities will be graded according to the NCI CTCAE version 4.03.

In all summaries, emphasis will be placed on treatment emergent adverse events (TEAEs), namely, those with initial onset or that worsen in severity after the first dose of study drug. Adverse events will be summarized by the frequency of patients experiencing treatment emergent adverse events corresponding to body systems and MedDRA preferred term and by worst NCI CTCAE (version 4.03) grade. Summaries will also be provided of treatment related TEAEs, namely, those judged by the investigator to be related or likely related to study drug.

Adverse events leading to death or discontinuation of study treatment, events classified as NCI CTCAE version 4.03 Grade 3 or higher, study drug related events, and serious adverse events will be considered with special attention. Adverse events reporting, including suspected unexpected serious adverse reactions, will be carried out in accordance with applicable local regulations.

9.4.4. Laboratory Test Abnormalities

The number and percentage of patients who experienced laboratory test abnormalities will be summarized according to worst toxicity grade observed for each lab assay, graded according to NCI CTCAE version 4.03. The analyses will summarize laboratory tests both on the entire study period and by cycle (Cycle 1 and Cycles beyond 1). Shift tables will be provided to examine the distribution of laboratory toxicities.

For laboratory tests without CTC grade definitions, results will be categorized as normal, abnormal or not done.

9.4.5. Baseline Characteristics

Patient characteristics at the time of study entry will be summarized in frequency tables and descriptive statistics will be provided for quantitative variables for the full analysis set (see [Section 9.2](#) for definitions of study populations).

9.4.6. Electrocardiogram Analysis

The QT measurements corrected by heart rate (QTc) will be used for the data analysis and interpretation. QTcF is planned to be the primary analysis method for the QTc endpoint. In addition a study-specific correction method (QTcS) and QTcB may also be evaluated for the QTc evaluable patients. The most appropriate correction method that eliminates any QT vs. RR relationship may be chosen after review of the data.

